Study title: Mindfulness and Diabetes Distress: Acceptability of Self-Led
Mindfulness-Based Intervention

Document Date: Study Protocol last approved by the University of Nevada, Reno
Institutional Review Board on 12/13/2019; Statistical Analysis Plan last approved
by the University of Nevada, Reno Institutional Review Board on 04/19/2018

1. Study Protocol

Objectives

This study had two primary aims. First, to examine the associations of mindfulness and diabetes-related outcomes, and second, to examine the acceptability, feasibility, and potential utility of self-led mindfulness-based stress reduction (MBSR) intervention.

Participants

Participants for the present study included a sample of 25 adolescents (14 females; 56%), 14-18 years old ($M= 16.25$, $SD= 1.6$ years) from urban and rural areas of Nevada. Most participants identified as White ($n=22$; 88%) and one participant as Asian, one participant as Native Hawaiian or Pacific Islander, and one participant as bi-racial. Participants reported a wide range of diagnosis length, ranging from less than a year to 16.15 years ($M=5.3$, $SD=4.1$). Nineteen participants reported using a continuous blood glucose monitor (76%) and 17 endorsed using an insulin pump (68%). Additionally, 10 participants reported that they qualify for free lunch at school (40%). Participants were asked to report on psychopathology and other medications that may impact attention for mindfulness activities. Inclusion criteria included being an adolescent (aged 13-19) with a type 1 diabetes diagnosis and currently attending school or being a recent high school graduate. Participants were excluded if they were a ward of the state, or had severe psychiatric disturbances (e.g., active psychosis) or severe developmental delay that hindered their ability to self-report. Participants were not excluded based on length of type 1 diabetes diagnosis. Trained undergraduate research staff screened participants for eligibility during the consent process.

Procedures

Procedures were approved by the Institutional Review Board at the University of Nevada, Reno. Electronic parental consent was obtained when the child was under the age of 18, in which case child assent was also obtained. Participants 18 and older provided electronic consent. Participants were recruited with flyers at a regional diabetes camp, flyers to community diabetes support groups, and direct recruitment by research staff in a local pediatric endocrinology clinic to obtain participants from both urban and rural areas of Nevada. Recruitment for this parallel pilot trial began in the fall of 2018 and completed in early spring 2020. All enrolled participants completed a baseline survey and were randomized to either begin the 10-week intervention period immediately or in 10-weeks. Based on prior studies of predictors of glycemic levels and treatment response, randomization was computerized and stratified based on gender, length since type 1 diabetes diagnosis (at or below 2 years versus more than 2 years) and most recent HbA1c (at or below 8.5% versus at or above 8.6%). After the baseline assessment and across the initial and waitlist intervention periods, participants also completed assessment questionnaires 10 weeks and 20 weeks after the study start date.

Research staff were trained by two graduate students on recruitment procedures and eligibility criteria. Sixty-four participants contacted our research staff indicating interest in participating in the study and provided permission to contact either online or in person (See Figure 1). During the study period, an interim study endpoint was reached where it was determined due to attrition and loss to follow-up as well as feedback from the enrolled participants ($n = 29$) that the intervention required revision to increase acceptability. Thus, enrollment was stopped prior to reaching the planned, per a priori power analyses, sixty participants. Of the 64 participants that indicated interested in the study, five participants

declined further screening and two participants were not eligible after screening. At the interim stop point, 29 participants had been consented and enrolled in the study. An additional 28 participants expressed interest in enrolling but did not complete the consent process before the interim study endpoint was reached. Among the 29 enrolled participants, 25 participants completed their baseline survey and were randomized to intervention now (n=15) or waitlist (n=10); groups were not balanced as enrollment was stopped early. Four of the 29 participants passively declined to complete the baseline survey and were not randomized. During the course of the study, two participants withdrew from the study after intake (reasons: busy with school, study participation was stressful), but nine were lost to follow-up at 10-weeks and another six were lost to follow-up at 20-weeks.

Intervention Program. The mindfulness-based intervention in the present study was delivered via a teen MBSR workbook and online communication across the 10-week intervention period. Participants were assigned weekly readings and activities from an MBSR workbook for teens (Biegel, 2017). Topics included understanding stress, introduction to mindfulness, mindful eating and other mindfulness-based principles and were recommended to be completed daily. Mindfulness-based exercises were either self-led per instructions provided in the workbook or to be completed using an audio recording directing participants' behaviors. Participants received emails twice per week with reminders about their assignments for the upcoming week and reminders to practice mindfulness daily. At the end of the week, participants received a reminder to complete a brief survey to obtain qualitative data regarding the acceptability of that week's content. Qualitative feedback regarding participants' acceptability of the workbook were used in analyses and included open-ended questions

regarding how helpful participants found each exercise and what hindered them from completing the exercises.

Participants could earn \$10 for each assessment questionnaire, \$10 for completing at least six of the ten weekly survey over the ten-week intervention period, and an additional \$10 for completing all 10 weekly surveys. Maximum earning for each participant was \$50. All measures were completed electronically through RedCap.

Measures

Mindful Attention Awareness Scale-Adolescent. The Mindful Attention Awareness Scale-Adolescent (MAAS-A; Brown et al., 2011), adapted from the MAAS for adults (Brown & Ryan, 2003), assesses dispositional mindfulness in adolescents. The MAAS-A has a single-factor structure with 14 items rated on a 6-point scale (1 = almost always, 6 = almost never). Higher scores indicate higher trait mindfulness. The MAAS-A has high internal consistency and test-retest reliability as well as both concurrent and incremental validity (Brown et al., 2011) with strong internal consistency in the study sample ($\alpha = .92$).

Self-Compassion Scale. The Self-Compassion Scale (SCS; Neff, 2003) is a 26-item measure that assesses different aspects of self-compassion in individuals 14 and older. Participants rate how often they engage in each self-compassionate behavior in specific situations (for example, “When I fail at something important to me, I try to keep things in perspective”). The SCS is rated on a 5-point scale (1 = almost never, 5 = almost always). Total score is calculated by computing the sum of all items. The SCS has been shown to have good internal consistency ($\alpha = 0.92$) and convergent validity with adolescents (Cunha, Xavier & Castilho, 2016) and had strong internal consistency in this sample ($\alpha = .95$).

Diabetes Distress. The Diabetes Stress Questionnaire (DSQ; Delamater et al., 2013) assesses different daily, diabetes-specific stressors. The measure consists of 65 items and includes eight subscales. Participants rate severity of stress across several diabetes-related scenarios on a 4-point scale (0 = not at all, 3 = very much). A total score is calculated by computing the mean of all items in addition to the mean score for each subscale. The DSQ has high internal consistency ($\alpha > 0.7$) and strong convergent validity ($0.46 < r > 0.77$; Kamody et al., 2014) and had strong internal consistency in this sample ($\alpha = .97$).

Health-related Quality of Life. The PedsQL 3.2 -Diabetes Module (PedsQL- DM; Varni et al., 2018) assesses diabetes-specific, health-related quality of life in children, adolescents, and young adults. Each item is rated on a 5-point scale (0 = never, 4 = almost always). Summary scores are calculated by computing the sum of all items divided by the total number of items answered. The PedsQL-DM has strong internal consistency and construct validity (Varni et al., 2018) and had strong internal consistency in this sample ($\alpha = .92$).

Perceived Stress. The Perceived Stress Scale-10 Item Version (PSS-10; Cohen, Kamarack, & Mermelstein, 1982) assesses the severity of broad, stressful situations. Participants rank how often each statement applies to their feelings of stress on a 5-point scale (0 = never, 4 = very often). Negative items are reversed and the sum of all 10 items is calculated. Higher scores indicate higher perceived stress. The PSS-10 has well-documented reliability and validity ($\alpha = 0.84$; Perera et al., 2017) and had strong internal consistency in this sample ($\alpha = .93$).

Psychosocial Impairment. The Pediatric Symptoms Checklist-17 (PSC-17; Gardner et al., 1999) assesses a child's psychosocial functioning. The present study uses the self-report PSC-17, consisting of three subscales. Participants rate how frequently each symptom occurs on a 3-

point scale (0 = never, 2 = often). Total scores range from 0-34 with higher scores indicating greater risk of psychosocial dysfunction. The PSC-17 has strong concurrent validity and high internal constancy ($\alpha = 0.89$; Murphy et al., 2016) and had sufficient internal consistency in this sample ($\alpha = .86$).

Diabetes Treatment Engagement. The Self Care Inventory (SCI), originally developed by La Greca et al. (1988), was modified to include eight additional items reflecting modern diabetes management behaviors (Helgeson et al., 2007). The SCI assesses to what degree individuals follow health care provider guidelines for diabetes-management behaviors. The investigators removed the item “how frequently do you come in for appointments” from the study as the measure was not used within a physician/ appointment context. After removing the item, the SCI consisted of 22 items and is rated on a 5-point scale (1 = never, 5 = always). A total score is calculated by computing the average of all of the items. The modified version of the SCI has high internal consistency ($\alpha = 0.78-0.82$) and is highly correlated with the original SCI (Helgeson et al., 2010) and had sufficient internal consistency in this sample ($\alpha = .88$).

Glycosylated hemoglobin percentage (HbA1c). At intake, participants self-reported their most recent HbA1c. Higher HbA1c percentages are associated with less optimal glycemic control in the past two to three months.

2. Statistical Analysis Plan

The aim of the present study was two-fold. First, to examine the association between mindfulness, diabetes distress, HbA1c, self-compassion, general perceived stress, diabetes treatment engagement, and diabetes-related quality of life, the investigators used baseline

assessment data from all randomized participants and conducted Pearson correlations.

Additionally, to inform what aspects of mindfulness are most connected with diabetes distress, the investigators explored the associations of each item on the MAAS-A scale with diabetes distress ratings. Second, to assess the feasibility, acceptability and utility of the self-led MBSR intervention for adolescents with type 1 diabetes the investigators examined attrition and the number of weekly surveys completed as well as feedback from the participants during the study.

To further consider the potential utility of the self-led MBSR intervention in this population, the investigators examined changes in the primary outcomes of mindfulness and diabetes related-stress at baseline and 10-week follow-up between the intervention and waitlist groups using independent sample t-tests and from pre-to post-intervention in high engagement participants (those who completed at least six of 10 weekly surveys) using paired sample t-tests. To limit bias from missing data at 10-week follow-up ($n = 11$) in independent sample t-tests an intent-to-treat approach was used, where the baseline level of mindfulness and diabetes-stress was used as the 10-week level for missing data rather than excluding those participants from analyses. The same intent to treat approach was used for the assessment of pre-to post-intervention changes in high engagement participants using paired sample t-tests.

References

Biegel, G. M. (2017). *The stress reduction workbook for teens: Mindfulness skills to help you deal with stress*. New Harbinger Publications.

Brown, K. W., & Ryan, R. M. (2003). The benefits of being present: Mindfulness and its role in psychological well-being. *Journal of Personality and Social Psychology*, 84(4), 822–848.
<https://doi.org/10.1037/0022-3514.84.4.822>

Brown, K. W., West, A. M., Loverich, T. M., & Biegel, G. M. (2011). Assessing adolescent mindfulness: Validation of an Adapted Mindful Attention Awareness Scale in adolescent normative and psychiatric populations. *Psychological Assessment*, 23(4), 1023–1033.
<https://doi.org/10.1037/a0021338>

Delamater, A. M., Patiño-Fernández, A. M., Smith, K. E., & Bubb, J. (2013). Measurement of diabetes stress in older children and adolescents with type 1 diabetes mellitus. *Pediatric Diabetes*, 14(1), 50–56. <https://doi.org/10.1111/j.1399-5448.2012.00894.x>

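### Does a pre-recruitment approval date on an SAP that already counts 11 missing outcomes call its analysis rules into question?

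*Combined protocol and SAP*

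**What the plan says.** The Document Date line gives two approval dates: the protocol by the "Institutional Review Board on 12/13/2019; Statistical Analysis Plan last approved" "by the University of Nevada, Reno Institutional Review Board on 04/19/2018". No version history or later SAP approval is given.

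Under Procedures, the protocol states: "Recruitment for this parallel pilot trial began in the fall of 2018 and completed in early spring 2020". The same section reports 25 participants randomized (15 immediate, 10 waitlist), two withdrawals after intake, and that "nine were lost to follow-up at 10-weeks".

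The Statistical Analysis Plan section is in the past tense. It introduces its missing-data rule with "To limit bias from missing data at 10-week follow-up ($n = 11" and says that "the baseline level of mindfulness and diabetes-stress was used as the 10-week level for missing data". It applies the same rule to paired t-tests in participants who completed at least six of the ten weekly surveys. For the baseline aim it says that "the investigators explored the associations of each item on the MAAS-A scale with diabetes distress ratings".

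**The concern.** A plan approved in April 2018 cannot contain a count of outcomes that went missing later. The printed text therefore differs from the approved text in at least that respect, and nothing marks what else was added. A reader who takes the date at face value may believe that the carry-forward rule and the high-engagement paired tests were fixed before recruitment.

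The carry-forward rule sets a large share of the 10-week data, and the SAP names mindfulness and diabetes-related stress as primary outcomes. If the rule had been chosen after the outcomes were seen, the p-values of the group comparison could be read only as exploratory.

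**Working it through.** **Reproducing the SAP's own figure.** Inputs from Procedures: 2 withdrawals after intake, 9 lost at 10 weeks, 25 randomized.

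- Missing at 10 weeks: 2 + 9 = 11, which matches the SAP.
- Observed at 10 weeks: 25 − 11 = 14.
- Share carried forward: 11/25 = 44%.
- Participant flow: 64 − 5 − 2 − 28 = 29 enrolled; 29 − 4 = 25 = 15 + 10 randomized. The counts are consistent, so 11 is the realised number and not a planning assumption.

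**Dates.** The documents say only fall 2018, so the start is an assumption: 1 September or 22 September.

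- 19 April to 1 September 2018 is 135 days; adding 10 weeks (70 days) gives 10 November 2018, 205 days after the SAP approval.
- 19 April to 22 September 2018 is 156 days; 156 + 70 = 226 days, which is 1 December 2018.

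On either assumption the count of 11 postdates the approval by more than six months. That part of the concern is correct.

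**Is the mismatch peculiar to the SAP?** The protocol part was last approved on 12/13/2019 but reports recruitment completed in early spring 2020. It also gives sample means and SDs under Participants, attrition under Procedures, and in-sample reliability coefficients under Measures. Both parts have the same form: a retrospective account headed by the dates on which the underlying plans were last approved. This points to one later compilation and not to an analysis plan rewritten under an old date.

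**What can be said about each rule?**

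- *Carry-forward:* its sentence contains the count of 11. The count must be later; the rule itself could have been in the 2018 text without the count. The documents do not settle it.
- *High-engagement paired tests:* the six-of-ten cut-off is also the payment threshold in Intervention Program, where participants were paid for "completing at least six of the ten weekly survey over the ten-week intervention period". That speaks against a cut-off picked from outcomes, although it does not date its use as an analysis set.
- *Item-level MAAS-A associations:* the SAP already presents these as exploration, so an exploratory label would add nothing.

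**Would anything computed change?** No. The tests, the imputation rule and the analysis sets are stated, and an analyst who follows them gets the same numbers whether the text dates from 2018 or 2020.

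**The case for a change.** The strongest case for acting is that the date is the only evidence of prespecification, and it is attached to text that cannot be that old. A retrospective summary is acceptable, but it should carry its own date and separate planned rules from added ones. The carry-forward rule governs 44% of the 10-week values, and the comparison serves the stated aim of judging potential utility. Asking for the approved version costs little and could confirm that the rules were planned.

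Much of this stands as a comment on documentation. The timing of the carry-forward rule and of the paired tests is a fair question that the documents leave open. What does not stand is the step from undated to defective. The past tense and the reported missing count make it plain that the wording is retrospective, and no section calls the t-tests prespecified or confirmatory. The SAP introduces them as a further look at potential utility, in a pilot stopped at 25 randomized of 60 planned, so a careful reader would treat their p-values as exploratory in any case.

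Simulating how often carry-forward and observed-only analyses disagree would not close the gap. It needs assumed inputs, such as the split of missing values by arm, the correlation over time and the effect size. It also measures the difference between two methods, not when one of them was chosen.

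**Conclusion.** The dating mismatch is real: 11 missing outcomes are counted in text headed by an approval at least 205 days before the first possible 10-week assessment, assuming recruitment began no earlier than 1 September 2018. It shows that the printed wording was written or edited later. It does not show that any rule was chosen after data were seen, and the approved 2018 version is not available to test that.

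The remaining gap is one of provenance, of low severity, and it applies equally to the protocol part. The sponsor could close it by dating the compilation and listing what was added to each part; only if the carry-forward rule or the paired tests proved absent from the 2018 text would a post hoc label be due. No analysis rule, number or method in the plan needs to change on this ground.

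### The between-arm t-tests leave out the three stratification factors: a minor and conservative loss of precision, and only if 10-week scores (not change scores) are tested

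*Combined protocol and SAP*

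**What the plan says.** **Study Protocol, Procedures.** The document states that "randomization was computerized and stratified based on gender, length since type 1 diabetes diagnosis" and HbA1c, with the last two dichotomised as "at or below 2 years versus more than 2 years) and most recent HbA1c (at or below 8.5% versus at or above 8.6"%. That makes three binary factors and up to eight strata. The reason given is "Based on prior studies of predictors of glycemic levels and treatment response". Block size is not stated. The arms ended as "randomized to intervention now (n=15) or waitlist (n=10); groups were not balanced as enrollment was stopped early".

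**Statistical Analysis Plan, final paragraph.** Changes in mindfulness (MAAS-A) and diabetes stress (DSQ), at baseline and 10 weeks, are compared "between the intervention and waitlist groups using independent sample t-tests". The wording does not settle whether the tested quantity is the 10-week score or the change from baseline. For the missing 10-week values (n = 11), "the baseline level of mindfulness and diabetes-stress was used as the 10-week level for missing data". No covariate, stratified test or model using the three factors appears anywhere. Alpha and sidedness are not stated.

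**The concern.** Stratified allocation with balance inside strata removes part of the chance difference between arms in the stratifying factors. A plain two-sample t-test takes its standard error from the total within-arm variance, so it still counts the variation that the design removed. Where the factors predict the outcome, the standard error is too large: intervals are too wide and the test rejects a true null less often than its nominal level. The direction is conservative, so false positives are not inflated. What is at stake is precision in a trial of 25, and a possible understatement of the potential utility that the second aim sets out to explore.

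**Working it through.** **The plan's own figure.** The only design figure is the planned 60: "enrollment was stopped prior to reaching the planned, per a priori power analyses, sixty participants". No effect size, SD, alpha or power accompanies it, so it can only be solved backwards. With 30 per arm and two-sided 5%, d = (z for alpha + z for power) × √(2/30). This gives 2.802 × 0.258 = 0.72 at 80% power and 3.242 × 0.258 = 0.84 at 90%. The 60 is therefore neither confirmed nor refuted.

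**Inputs from the documents.** 15 v 10 randomised; three binary factors; 56% female; 11 of 25 missing at 10 weeks.

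**Assumptions.** Two-sided 5%; duration split 25/75; HbA1c split 50/50; blocks of 2, 4 or 6 within strata; the factors contribute equally to R², the share of outcome variance explained, which is varied because the documents give no value.

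**Closed-form check, outcome SD 1.**
- √(1/15 + 1/10) = 0.408.
- t-test half-width: 2.069 (23 df) × 0.408 = 0.84 SD, whatever the R².
- Model with three factors, perfectly balanced: 2.086 (20 df) × 0.408 × √(1 − R²). This gives 0.85 at R² = 0, 0.76 at 0.2 and 0.71 at 0.3. Residual imbalance makes the simulated values slightly larger.

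**Simulated 95% half-width on 10-week scores, 15 v 10, blocks of 4, no carry-forward.**

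| R² | t-test | with three factors |
|---|---|---|
| 0 | 0.84 | 0.87 |
| 0.1 | 0.84 | 0.82-0.83 |
| 0.2 | 0.84 | 0.78 |
| 0.3 | 0.84 | 0.73 |

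Full widths at R² = 0 were 1.671 and 1.735, a ratio of 1.038. The model therefore breaks even near R² = 1 − (1.671/1.735)² = 0.07.

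**Type I error of the t-test, given 15 v 10.**

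| Allocation | R² = 0.1 | R² = 0.3 | R² = 0.5 |
|---|---|---|---|
| Blocks of 2 | 4.6% | 2.6% | 1.5% |
| Blocks of 4 | 3.7% | 2.9% | 2.0% |
| Blocks of 6 | 4.7% | 3.7% | 2.7% |
| Unrestricted | 5.4% | 5.7% | 5.6% |

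Separate runs with blocks of 4 gave 3.4-4.1% at R² = 0.2 and 2.7-3.9% at R² = 0.3. Monte Carlo error is about 0.3 points: √(0.035 × 0.965/3,000) = 0.0034. With blocks of 4 the factor-adjusted model stayed at about 4.4-5.5% throughout. The unrestricted row shows that the effect comes from balance within strata and not from prognostic factors alone.

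**Change scores.** A baseline score was added (assumed within-stratum correlation 0.5 or 0.7), with equal factor effects at both times, carry-forward for 11 of 25 missing at random, and R² = 0.2. Half-widths at the two correlations:
- Change-score t-test: 0.55 / 0.43 SD, with type I error 5.1% / 4.9%.
- 10-week score on arm and factors, no baseline: 0.77 / 0.78 SD. That is 0.77/0.55 = 1.40 and 0.78/0.43 = 1.81 times as wide.
- 10-week score on arm and baseline: 0.53 / 0.43 SD. Adding the three factors gives 0.55 / 0.44 SD.

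Part of that narrowness is produced by carry-forward itself. Without it, the change-score t-test gives 0.75 / 0.58 SD against 0.78 / 0.78 SD for the model with factors but no baseline.

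**The case against.** The strongest objection is that the plan may intend a t-test of change scores. A factor with the same effect at both times then drops out, the test holds about 5%, and a model with the factors but no baseline score would lose precision. This stands. It makes the point conditional and requires baseline in the remedy.

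Second, once baseline is in the model the factors add almost nothing at n = 25. This also stands. What remains is agreement between analysis and randomisation.

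Third, a reader might infer that the protocol itself assumes the factors predict these outcomes. It does not: the stated rationale concerns glycemic levels and treatment response, not the level of mindfulness or diabetes stress. A predictor of response may also be an effect modifier, which main effects do not address.

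Fourth, tight balance within strata is not established. In simulation an imbalance of five or more occurred in about 3% of trials with blocks of 2, 11% with blocks of 4 and 42% with unrestricted allocation. Against this, the document blames the 15:10 split on early stopping, which suggests that balance was expected at completion, and the conservatism persists given 15 v 10.

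The argument that 25 is too few for covariates is weaker. Arm, baseline and three binary main effects leave 25 − 6 = 19 error degrees of freedom.

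**Conclusion.** The mismatch is real: the design stratifies on three factors and the between-arm analysis uses none of them. It matters only if 10-week scores are tested, allocation was balanced within strata, and the factors predict MAAS-A or DSQ. Then the t-test runs at about 3-4% instead of 5% at R² of 0.2-0.3, and its interval is about 8% (0.84/0.78) to 15% (0.84/0.73) wider than that of the factor-adjusted model. At R² = 0.1 the effect is small, and below about 0.07 factor adjustment alone widens the interval.

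A reader might infer that the test falls below its nominal level whenever the factors predict the outcome. The documents do not support this, because it fails for change scores with stable factor effects and for unrestricted allocation. Block size, R², alpha, and the duration and HbA1c splits are assumptions. The figures on 10-week scores also leave out the baseline carry-forward, which is a separate problem.

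This is a minor precision point in a stopped pilot, where the t-tests are a supplementary look at utility and the error is conservative.

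**What to change.** In the final paragraph of the Statistical Analysis Plan, replace the two between-arm t-tests (MAAS-A and DSQ) with a linear model of the 10-week score on arm, the same scale's baseline score, and gender, diagnosis length and HbA1c group as three binary main effects, not eight stratum cells. Report the adjusted difference with its 95% interval. Keep the unadjusted t-test as secondary, and say whether it uses 10-week or change scores. Because recruitment is complete, record that the model was specified afterwards.

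Baseline must not be omitted: without it the model can be much wider than a change-score t-test.

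The cost is one sentence and a re-run. The three factors were needed to randomise and baseline scores were collected before allocation, so no new data are required. The statistical price of the factors is three degrees of freedom, up to about 4% in width at n = 25 once baseline is included.

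### Does leaving attrition undefined by arm and period, in a waitlist design, undermine the assessment of acceptability?

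*Combined protocol and SAP*

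**What the plan says.** The second primary aim (section 1, Objectives) covers acceptability, feasibility and potential utility. For this aim section 2 says that "to assess the feasibility, acceptability and utility of the self-led MBSR intervention for adolescents with type 1 diabetes the investigators examined attrition", and in the same sentence adds two further measures: the number of weekly surveys completed and participants' feedback. Attrition is given no time point, arm or base.

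Under section 1, Procedures, participants were "randomized to either begin the 10-week intervention period immediately or in 10-weeks", 15 to the immediate start and 10 to the waitlist. Enrolment ended early "due to attrition and loss to follow-up as well as feedback from the enrolled participants"; the conclusion drawn was "that the intervention required revision to increase acceptability". Losses are given for both arms together: two withdrawals after intake, for school workload and because taking part was stressful, and then "nine were lost to follow-up at 10-weeks and another six were lost to follow-up at 20-weeks". The Procedures also cite Figure 1 for participant flow; its content is not available here. Section 2 gives one pooled count, n = 11, for missing 10-week data.

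**The concern.** The start is staggered. At the 10-week assessment the waitlist arm had not begun the workbook. Between weeks 10 and 20 the immediate-start arm had passed its ten-week programme. A loss rate pooled over arms therefore mixes loss while waiting, loss during the programme and loss after it. Only the second bears on whether the workbook is acceptable; the other two bear on keeping adolescents in a study. Because attrition is a named measure for a primary aim, and was cited when the intervention was judged to need revision, a reader might take a pooled percentage as evidence against the workbook when an unknown share of the losses happened outside any intervention period.

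**Working it through.** **Inputs.** From section 1, Procedures: 15 + 10 = 25 randomised; 2 withdrew; 9 lost at 10 weeks; another 6 at 20 weeks. From section 2: 11 with missing 10-week data.

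**The plan's own figure.** 2 + 9 = 11, which matches n = 11. As a share, 11/25 = 44% (exact 95% interval 24.4% to 65.1%).

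**By 20 weeks.** 11 + 6 = 17, and 17/25 = 68%. Neither percentage is printed in the documents; both are computed here from the counts.

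**What the pooled counts allow.** Let x be the immediate-start losses by week 10, so that waitlist losses are 11 − x. Let y be the waitlist losses among the later six. Waitlist participants still present at week 10 number 10 − (11 − x) = x − 1. Loss during participants' own intervention period is

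(x + y) / (15 + x − 1).

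This rests on assumptions the documents do not state: both withdrawals came before week 10, nobody lost at 10 weeks came back, all 15 immediate-start participants began, and waitlist participants missing at 10 weeks never began. The last one sets the denominator. If those participants did begin, the base moves towards 15 + 10 = 25.

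- *Arithmetic limits.* There are 53 feasible pairs (x, y). The lowest rate is x = 1, y = 0: 1/15 = 7%. The highest is x = 11, y = 6: 17/25 = 68%.
- *How far to trust the floor.* It needs all 10 waitlist participants and only 1 of the 15 others lost by week 10. If loss were unrelated to arm, that split has probability C(15,1) × C(10,10) / C(25,11) = 15/4,457,400, about 3 in a million. It is a limit, not a scenario.
- *Narrower assumption, 2 to 6 waitlist losses by week 10.* Lowest: x = 5, y = 0, giving 5/19 = 26%. Highest: x = 9, y = 6, giving 15/23 = 65%.
- *Roughly equal loss by arm.* 7/15 and 4/10 by week 10, then 3/8 and 3/6. Intervention-period loss is (7 + 3)/(15 + 6) = 10/21 = 47.6%. The losses outside any intervention period are 4 + 3 = 7 of 17, or 41%.

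In the equal-loss case the intervention-period rate differs from the pooled 10-week rate by 47.6 − 44.0 = 3.6 points. The exact interval on 11/25 is itself 65.1 − 24.4 = 40.7 points wide.

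**Does anything else in the plan use the definition?** The between-group t-tests use the 10-week time point and the baseline value for the 11 missing. The high-engagement analysis uses six of ten weekly surveys. Neither refers to attrition as a rate, and the documents give no numerical stopping threshold based on it.

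**The case for a change.** The strongest case for a change is that the inference was actually drawn: attrition helped lead to the view that the intervention needed revising. In 52 of the 53 feasible splits at least one loss falls outside any intervention period, and even with 2 to 6 waitlist losses by week 10, between 2 and 12 of the 17 losses do. A flow figure, even one split by arm, would not say which losses the plan counts as evidence on the workbook. The remedy would be one sentence and a small table from data already held.

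Part of this stands. The counts in the text cannot tell a reader how many adolescents left while using the workbook, and 68% in particular should not be read that way.

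What does not stand is the step from there to a fault in the plan. Section 2 does not commit to a pooled rate, so no stated rule yields a wrong answer. With an arm split, the 10-week data give immediate-start loss in weeks 0 to 10 directly. The revision decision also cited participant feedback, and the Intervention Program text says the open-ended questions asked how helpful each exercise was and what got in the way of completing it. The withdrawal reasons support neither reading: for someone in the immediate-start arm, stressful participation could include the workbook, and the arm is not given.

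**Conclusion.** No change to the plan follows. Attrition is left without arm, period or denominator, which is a gap in description that analysts fill in the ordinary course by reporting loss by arm and by period. Its likely effect is small at 10 weeks: 48% against 44% if loss is about equal in the two arms. It could be larger if the arms differ, with 26% to 65% for 2 to 6 waitlist losses by week 10. Those figures depend on the assumed split and on waitlist participants missing at 10 weeks never having begun, so they show what the counts permit and are not estimates for this trial. With 25 randomised participants, finer cells would be very imprecise; for instance, an assumed 4/10 has an exact interval of 12% to 74%. Writing the definition into the plan would alter no test, estimate or conduct of the trial, and two of the three measures for this aim already bear directly on the workbook.
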